6.1 Study Procedures/Evaluations

6.1.1 Study Specific Procedures

- Imaging assessment with knee MRA (visits 2, 6, and 8):
 - Baseline and follow-up (at 6 and 24 months) knee MRA will be performed.
- Biological specimen collection (visits 2, 5, 6, 7, and 8):
 - Baseline and follow-up biomarker analysis from blood, urine, and knee aspirate (synovial fluid) will be obtained from participants.
- Administration of questionnaires or other instruments for patient-reported outcomes (visits 2, 5, 6, 7, and 8):
 - VAS questionnaire
 - KOOS questionnaire
 - Self-reported quality of life EQ-5D-5L questionnaire
 - Anchor pain questionnaire
- GAE procedure (visit 3)
- Medical history (visits 2, 5, 6, 7, and 8):
 - Complete medical history will be obtained from medical records if available and/or by interview during clinic visits.
- History of previous and concomitant treatment (visits 2, 5, 6, 7, and 8):
 - Knee injections and frequency
 - Medication history. Will focus on medications currently taken for the treatment of knee pain; including prescription and over-the-counter medications for pain.
 - Physical therapy and frequency
 - Weight loss / gain
- Focused physical examination (visits 2, 5, 6, 7, and 8):
 - Vital signs (temperature, blood pressure, heart rate, oxygen saturation, height, weight, BMI)
 - Focused knee examination.

Note: A discussion of the results of any study specific procedures (e.g., radiographic or other imaging or laboratory evaluations) will be provided to participant after the completion of the study unless this information represents a significant health-related issue.

6.1.2 Standard of Care Study Procedures

- Standard of care imaging assessment with knee radiograph (visit 2):
 - Knee radiograph obtained within 3 months of the screening will be used to assess the knee.
 - A new knee radiograph will be obtained during or prior to visit 2 if no recent (within 3-month) radiograph of the target knee is available
 - Knee radiograph protocol: AP weightbearing, lateral, sunrise views
 - Knee radiographs will be assessed by a IRB-approved musculoskeletal radiologist

6.2 Laboratory Procedures/Evaluations

Baseline and follow-up biospecimen collection will be performed on visits (2, 5, 6, 7, and 8). Urine samples, peripheral venous blood draws, and knee aspirates (synovial fluid) will be obtained. Approximately 10 cc of blood will be collected from peripheral venous blood in each visit that requires collection of blood samples.

The samples will be sent to the NYU orthopedic lab for biomarker analysis.

- Storage location: These samples collected as part of the approved research protocol are stored and identified by barcodes and collection date only and kept in the NYU Langone Orthopedic Hospital.
- Access to samples: IRB-approved study team members from NYU Langone Orthopedic Hospital have access to these samples.
- Protecting subject anonymity: Study team members who have access to the samples will receive the biospecimen tubes labeled with study subject number and date of collection.
- Samples will be stored until the end of data analysis and study closure.

6.2.1 Other Assays or Procedures

Knee aspiration will be performed during baseline (visit 2) and follow-up visits (visits 5-8) when knee effusion is present to obtain synovial fluid for biomarker analysis. Baseline knee aspiration can be performed on the day of the procedure (visit 3) at the discretion of the investigator to minimize patient discomfort and pain as long as it's performed prior to the embolization. The procedure will be performed in the interventional radiology clinic, interventional radiology suite, or orthopedic clinic by an IRB-approved investigator after administration of local anesthetic. A needle will be advanced into the knee joint and approximately 10 cc of synovial fluid will be obtained and sent to the NYU orthopedic lab for biomarker analysis for later analysis (see section 6.2 for details of sample storage).

6.2.2 Specimen Preparation, Handling, and Storage

These samples (biospecimen) collected as part of the approved research protocol are stored and identified by barcodes and collection date only and kept in the NYU Langone Orthopedic Hospital. Processing and analysis will be performed by the biomarkers' lab.

6.2.3 Specimen Shipment

Specimen will be transferred to the biomarkers lab on the day samples are collected by an IRB-approved study coordinator in person.

6.3 Study Schedule

6.3.1 Screening (visit 1; Day -30 to -2)

In rheumatology, orthopedic, or vascular and interventional radiology clinic

- Obtain informed consent of potential subject
- Provide a copy of informed consent and key information sheet to subject
- Review subject's eligibility based on eligibility criteria
- Schedule study visits for eligible participants

Note: if subject prefers, visits 1 and 2 can be combined and procedures of these visits may be performed on the same day after completion of screening and obtaining informed consent.

Those candidates who are disqualified from study entry will be logged into the Screening Log with a reason for no study entry. A copy of the consent will be provided to the subject and the original filed in the study files.

6.3.2 Enrollment/Baseline (visit 2, Day -30 to -1)

- Obtain medical history, concomitant medications, demographics information
- Targeted physical exam
- Administration of study questionnaires
- Previous / concomitant treatments
- Baseline MRA (if one is not available within the last 3 months)
- Baseline knee radiograph (if one is not available within the last 3 months)
- Biospecimen collection (including knee aspiration for synovial fluid collection)

6.3.3 Interventional visit (visit 3, Day 0)

- Performed within 30 days of visit 2
- Geniculate artery embolization (GAE) procedure
- Record any immediate complications / adverse events detected during the procedure or observation period (if applicable)
- Subjects will be given a phone number to reach a physician 24 hours a day to report any adverse symptoms and receive medical advice

6.3.4 Follow up Visits:**6.3.4.1 Follow up safety visit (Visit 4; day 7 ± 3 days)**

- Subjects will be seen in clinic (in-person or telemedicine) or contacted by phone per subject's preference on day 7(± 3 days). As most complications of the procedure will be evident within this period, this visit is to evaluate for early AE's. If AE is suspected based on change in pain scores, functionality, or other signs / symptoms, further assessment and management will be performed based on the nature and severity of suspected AE.

6.3.4.2 Follow up visit at 3-month (Visit 5, Day 90 ± 10 days)

- Obtain medical history
- Record adverse events as reported by participant or observed by investigator (if applicable)
- Targeted physical exam
- Administration of study questionnaires
- Previous / concomitant treatments, including medical history
- Biospecimen collection (including knee aspiration for synovial fluid collection)

6.3.4.3 Follow up visit at 6 months (Visit 6, Day 180 ± 20 days)

- Obtain medical history
- Record adverse events as reported by participant or observed by investigator (if applicable)
- Targeted physical exam
- Administration of study questionnaires
- Previous / concomitant treatments, including medical history
- Biospecimen collection (including knee aspiration for synovial fluid collection)
- Follow-up knee MRA

6.3.4.4 Follow up visit at 12 months (Visit 7, Day 360 ± 30 days)

- Obtain medical history
- Record adverse events as reported by participant or observed by investigator (if applicable)
- Targeted physical exam
- Administration of study questionnaires
- Previous / concomitant treatments, including medical history
- Biospecimen collection (including knee aspiration for synovial fluid collection)

6.3.4.5 Follow up visit at 24 months (Visit 7, Day 720 ± 40 days)

- Obtain medical history
- Record adverse events as reported by participant or observed by investigator (if applicable)
- Targeted physical exam
- Administration of study questionnaires
- Previous / concomitant treatments, including medical history
- Biospecimen collection (including knee aspiration for synovial fluid collection)
- Follow-up knee MRA

6.3.5 Withdrawal/Early Termination Visit

- Obtain medical history
- Record adverse events as reported by participant or observed by investigator (if applicable)

- Targeted physical exam
- Administration of study questionnaires
- Previous / concomitant treatments, including medical history
- Biospecimen collection (including knee aspiration for synovial fluid collection)

6.3.6 Unscheduled Visit

Unscheduled visits if needed will be documented in the medical chart of the subject including the reason for the visit and assessment / management plan as determined by the visit.

6.4 Concomitant Medications, Treatments, and Procedures

All relevant concomitant medications taken during study participation, as well as treatments and procedures will be recorded. Medications to be reported are concomitant prescription medications, over-the-counter medications and non-prescription medications used pain management. For this protocol, a prescription medication is defined as a medication that can be prescribed only by a properly authorized/licensed clinician.

6.5 Justification for Sensitive Procedures

Not applicable.

6.5.1 Precautionary Medications, Treatments, and Procedures

Not applicable.

6.6 Prohibited Medications, Treatments, and Procedures

Not applicable.

6.7 Prophylactic Medications, Treatments, and Procedures

Not applicable.

6.8 Rescue Medications, Treatments, and Procedures

In the event of non-target embolization during the procedural visit leading to limb ischemia, subsequent interventions and / or medical management may be required for treatment of limb ischemia as medically indicated based on standard medical practice for treatment of limb ischemia.

6.9 Participant Access to Study Agent at Study Closure

After participants are no longer enrolled in the study, they will return to standard of care treatment for knee pain.

7 Assessment of Safety

7.1 Specification of Safety Parameters

Safety parameters include the number, severity, causality, timing, and description of complications, adverse events, or poor outcomes that are secondary to the procedure.

7.1.1 Definition of Adverse Events (AE)

An **adverse event** (AE) is any symptom, sign, illness or experience that develops or worsens in severity during the course of the study. Intercurrent illnesses or injuries should be regarded as adverse events. Abnormal results of diagnostic procedures or studies on target knee in the follow-up period after the study intervention are also considered to be AEs if the abnormality:

- results in study withdrawal
- is associated with a serious adverse event
- is associated with clinical signs or symptoms
- leads to additional treatment or to further diagnostic tests
- is considered by the investigator to be of clinical significance

7.1.2 Definition of Serious Adverse Events (SAE)

Adverse events are classified as serious or non-serious. A **serious adverse event** is any AE that is:

A **serious adverse event** is any AE that is:

- fatal
- life- or limb- threatening
- requires or prolongs hospital stay
- results in persistent or significant disability or incapacity
- a congenital anomaly or birth defect
- an important medical event

Important medical events are those that may not be immediately life or limb threatening but are clearly of major clinical significance. They may jeopardize the subject and may require intervention to prevent one of the other serious outcomes noted above.

All adverse events that do not meet any of the criteria for serious should be regarded as ***non-serious adverse events***.

7.1.3 Definition of Unanticipated Problems (UP)

Unanticipated adverse device effect, any serious adverse effect on health or safety or any life-threatening problem or death caused by, or associated with, a device, if that effect, problem, or death was not previously identified in nature, severity, or degree of incidence in the investigational plan or application, or any other unanticipated serious problem associated with a device that relates to the rights, safety, or welfare of subjects (21 CFR 812.3(s)).

Unanticipated Problems Involving Risk to Subjects or Others

Any incident, experience, or outcome that meets all of the following criteria:

- Unexpected in nature, severity, or frequency (i.e. not described in study-related documents such as the IRB-approved protocol or consent form, the investigators brochure, etc)
- Related or possibly related to participation in the research (i.e. possibly related means there is a reasonable possibility that the incident experience, or outcome may have been caused by the procedures involved in the research)
- Suggests that the research places subjects or others at greater risk of harm (including physical, psychological, economic, or social harm).

This definition could include an unanticipated adverse device effect, any serious adverse effect on health or safety or any life-threatening problem or death caused by, or associated with, a device, if that effect, problem, or death was not previously identified in nature, severity, or degree of incidence in the investigational plan or application (including a supplementary plan or application), or any other unanticipated serious problem associated with a device that relates to the rights, safety, or welfare of subjects (21 CFR 812.3(s)).

7.2 Classification of an Adverse Event

7.2.1 Severity of Event

The Investigator will assess the severity (intensity) of each adverse event as mild, moderate, severe, life-threatening / disabling event, or death / unexpected pregnancy abortion. The investigator will also categorize each adverse event as to its potential relationship to study device.

The severity and causality of all adverse events will be graded according to the new adverse event classification by the Society of Interventional Radiology Standards of Practice Committee [62], as follows:

- **Mild AE:** No therapy or nominal (non-substantial) therapy (postprocedural imaging performed and fails to show manifestation of AE); near miss (e.g., wrong site of patient prepared, recognized and corrected before procedure, wrong patient information entered for procedure);
- **Moderate AE:** moderate escalation of care, requiring substantial treatment, e.g., intervention (description of intervention and result of intervention) under conscious sedation, blood product administration, extremely prolonged outpatient observation, or overnight admission after outpatient procedure not typical for the procedure (excludes admission or hospital days unrelated to AE);
- **Severe AE:** marked escalation of care, i.e., hospital admission or prolongation of existing hospital admission for > 24 hours, hospital admission that is atypical for the procedure, inpatient transfer from regular floor/telemetry to intensive care unit, or complex intervention performed requiring general anesthesia in previously non-intubated patient (generally excludes pediatrics or in circumstances in which

general anesthesia would primarily be used in lieu of conscious sedation, e.g., in mentally challenged or severely uncooperative patients);

- **Life-threatening or disabling event:** e.g., cardiopulmonary arrest, shock, organ failure, unanticipated dialysis, paralysis, loss of limb or organ;
- **Patient death or unexpected pregnancy abortion.**

7.2.2 Relationship to Study Agent

For all collected AEs, the clinician who examines and evaluates the participant will determine the AE's causality based on temporal relationship and his/her clinical judgment. The degree of certainty about causality will be graded using the categories below according to the new adverse event classification by the Society of Interventional Radiology Standards of Practice Committee

- **Category 1:** AE not caused by procedure. The AE is completely independent of study drug administration, and/or evidence exists that the event is definitely related to another etiology. There must be an alternative, definitive etiology documented by the clinician.
- **Category 2:** Unknown whether AE was caused by the procedure.
- **Category 3:** AE caused by the procedure. There is clear evidence to suggest a causal relationship, and other possible contributing factors can be ruled out.

The definition implies a reasonable possibility of a causal relationship between the event and the study device. This means that there are facts (evidence) or arguments to suggest a causal relationship.

The following factors should also be considered:

- The temporal sequence from study procedure: The event should occur after the study procedure. The length of time from study procedure to event should be evaluated in the clinical context of the event.
- Underlying, concomitant, intercurrent diseases: Each report should be evaluated in the context of the natural history and course of the disease being treated and any other disease the patient may have.
- Concomitant procedures / treatments: The other drugs the patient is taking or the treatment the patient receives should be examined to determine whether any of them might be recognized to cause the event in question.
- Known response pattern for this class of study procedure: Clinical and/or nonclinical data may indicate whether a particular response is likely to be a class effect.
- Exposure to physical and/or mental stresses: The exposure to stress might induce adverse changes in the recipient and provide a logical and better explanation for the event.

7.2.3 Expectedness

The PI will be responsible for determining whether an AE is expected or unexpected. An AE will be considered unexpected if the nature, severity, or frequency of the event is not consistent with the risk information previously described for the study device.

7.3 Time Period and Frequency for Event Assessment and Follow-Up

The occurrence of an AE or SAE may come to the attention of study personnel during study visits and interviews of a study participant presenting for medical care, or upon review by one of investigators. All AEs including local and systemic reactions not meeting the criteria for SAEs will be captured on the appropriate eCRF. Information to be collected includes event description, time of onset, clinician's assessment of severity, relationship to study procedure (assessed only by those with the training and authority to make a diagnosis), and time of resolution/stabilization of the event. All AEs occurring while on study must be documented appropriately regardless of relationship. All AEs will be followed to adequate resolution.

Any medical condition that is present at the time that the participant is screened will be considered as baseline and not reported as an AE. However, if the study participant's condition deteriorates at any time during the study, it will be recorded as an AE. UPs will be recorded in the data collection system throughout the study.

Changes in the severity of an AE will be documented to allow an assessment of the duration of the event at each level of severity to be performed. AEs characterized as intermittent require documentation of onset and duration of each episode.

The PI will record all reportable events with start dates occurring any time after informed consent is obtained until 7 (for non-serious AEs) or 30 days (for SAEs) after the last day of study participation. At each study visit, the investigator will inquire about the occurrence of AE/SAEs since the last visit. Events will be followed for outcome information until resolution or stabilization.

All unresolved adverse events should be followed by the investigator until the events are resolved, the subject is lost to follow-up, or the adverse event is otherwise explained. At the last scheduled visit, the investigator should instruct each subject to report any subsequent event(s) that the subject, or the subject's personal physician, believes might reasonably be related to participation in this study. The investigator should notify the study sponsor of any death or adverse event occurring at any time after a subject has discontinued or terminated study participation that may reasonably be related to this study. The sponsor should also be notified if the investigator should become aware of the development of cancer or of a congenital anomaly in a subsequently conceived offspring of a subject that has participated in this study.

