and then every 6 months for a maximum of 4 years. Mean WOMAC pain scores significantly decreased from baseline to 1, 4, 6, 12, and 24 months after treatment (12.1 vs 6.2, 4.4, 3.7, 3.0, and 2.6; all $P < .001$). The WORMS score was evaluated at baseline and at 2 years after embolization in 35 knees and showed significant improvement of synovitis vs baseline ($P < .0016$) and no osteonecrosis or other evidence indicating aggressive progression of degenerative changes. There were no major AEs related to the procedures. Specifically, there was no incidence of tissue necrosis, dermal ulcers, or peripheral paresthesia in any embolized territory during the follow-up period. Moderate subcutaneous hemorrhage at the puncture site in 12 patients resolved within 1 week. Four of seven patients treated with Embozene showed transient cutaneous color change on the treated knee, which resolved spontaneously within 1 month.

A study by Bagla et.al, showed improvement in the pain scores in 20 patients with knee osteoarthritis. The mean VAS improved from $76 \text{ mm} \pm 14$ at baseline to $29 \text{ mm} \pm 27$ at 6-month follow-up ($P < .01$). The mean WOMAC score improved from 61 ± 12 at baseline to 29 ± 27 at 6-month follow-up ($P < .01$). Self-limiting skin discoloration occurred in 65% patients and 10% of patients developed transient plantar sensory paresthesia [51].

A study by Padia S et al evaluated the safety and effectiveness of GAE in patients with knee OS (grades 2, 3, 4). Knee OA severity was grade 2 in 18% of the patients, grade 3 in 43%, and grade 4 in 40%. Technical success was achieved in 100% of the subjects. The WOMAC total and VAS pain scores decreased by 61% and 67% at 12 months from a median baseline of 52 (of 96) and 8 (of 10), respectively. Twenty-seven patients (68%) had a reduction of $\geq 50\%$ in both WOMAC total and VAS pain scores [40]. Multiple meta-analysis of the published data show consistent results, confirming the safety and efficacy of GAE for treatment of knee OA [40, 54-57].

A recent study by Taslakian et al, reported a clinical success rate of 83% of patients with knee OA post GAE [43]. The study also evaluated the role of GAE as a disease modifying treatment option for knee OA by assessing systemic disease-specific biomarkers. The study found decreased neuron growth factor (NGF levels) following GAE which may contribute to pain reduction and slowing of cartilage degeneration.

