7.6 Reporting Procedures – Notifying the FDA

The study sponsor (PI) is required to report certain study events in an expedited fashion to the FDA. These written notifications of adverse events are referred to as IND/IDE safety reports.

The following describes the IDE safety reporting requirements by timeline for reporting and associated type of event:

- **Within 10 working days** (via telephone or facsimile report)
Any study event that is:
 - associated with the use of the study device, and
 - unanticipated,
 - regardless of the seriousness of the event.
- **Within 5 working days** (via written report)
 - Protocol deviation to protect the life of the subject in emergency
 - Withdrawal of IRB approval
 - Lack of informed consent

Reporting Process

Adverse events may be submitted on FDA Form 3500A (MEDWATCH Form [available in study regulatory binders], or in a narrative format.

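### Relationship to the study device is required for every AE, for FDA reporting and for the halting rule, but it has no defined scale in 7.2.2 and no listed field in 7.3

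*Combined protocol and SAP*

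**What the plan says.** Section 7.2.1 states that the investigator will also "categorize each adverse event as to its potential relationship to study device". It then refers to a published interventional radiology classification for severity and causality.

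Section 7.2.2 is headed as relationship to the study agent. Its three categories are: not caused by the procedure, unknown whether caused by the procedure, and caused by the procedure. Category 1 also mentions administration of a study drug, although the trial has none. For Category 3 the text adds: "There is clear evidence to suggest a causal relationship, and other possible contributing factors can be ruled out". The paragraph after the scale says: "The definition implies a reasonable possibility of a causal relationship between the event and the study device".

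Section 7.3 describes the AE record: "Information to be collected includes event description, time of onset", then the clinician's severity assessment, "relationship to study procedure (assessed only by those with the training and authority to make a diagnosis", and time of resolution. Relationship to the device is not in the list.

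Three other provisions depend on the device. The FDA timeline in 7.6 covers events that are "associated with the use of the study device, and" unanticipated. The halting rule in 7.7 and 7.8 counts severe AEs judged *probably related* or *related* to the study device. The unanticipated adverse device effect in 7.1.3 is defined by causation by, or association with, a device.

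Section 9.4.4 plans the proportion of patients with each AE type and with any AE, with causality graded on the same classification.

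**The concern.** This is an IDE study of one embolic, used outside the indications listed in section 1.2. The first secondary objective (2.2) includes the causality of each AE. Section 1.4.1 keeps apart the harms of the device, of angiography and catheterization, and of sedation. The causality scale merges them: a puncture-site hematoma and a skin change from microspheres would both be caused by the procedure.

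The device judgement is therefore ordered but has no instrument. Assessors must make it without defined levels, and nothing listed in 7.3 shows where it is stored. Decisions under 7.6, 7.7 and 7.8 would rest on a judgement that cannot be traced to the AE data.

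The two standards in 7.2.2 add a second uncertainty. The protocol calls post-TKA pain multifactorial (1.1 and 1.3). An assessor who needs other factors excluded could grade a new knee symptom Category 2, while one who accepts a reasonable possibility could grade it Category 3.

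**Working it through.** The plan states no figure that depends on this point, so there is none to reproduce. The check is a comparison of sections.

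| Section | What it needs or supplies | Relationship to |
|---|---|---|
| 7.2.1 | categorisation of every AE | device |
| 7.1.3 | unanticipated adverse device effect | device |
| 7.6 | FDA reporting | device |
| 7.7, 7.8 | halting rule | device |
| 7.2.2, Categories 1 to 3 | the only defined scale | procedure |
| 7.2.2, text after the scale | gloss on the definition | device |
| 7.3 | the only listed relationship item | procedure |

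**Step 1. Can the grade give device relationship?** Device-caused events are a subset of procedure-caused events, because the microspheres are delivered during the procedure. Category 1 therefore implies no device cause. Category 3 does not say whether the cause was the device, and Category 2 leaves it open.

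**Step 2. Can event type fill the gap?** In part. In 1.4.1 skin colour change and plantar paresthesia appear under the device, and access-site hematoma under catheterization. But infection, thrombosis and allergic reaction appear on both lists, and type alone cannot assign them.

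**Step 3. Is there one standard?** Category 3 asks for clear evidence with other factors excluded. The next paragraph speaks of a reasonable possibility. These are different thresholds, and they also have different objects: the procedure in the first, the device in the second.

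**Step 4. Do the halting terms map to the scale?** No. *Probably related* and *related* are not among the three categories, and the rule concerns the device.

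**Step 5. Illustration of size.** The inputs come from 1.2.2 and concern native-knee osteoarthritis. I assume that skin change and paresthesia count as device events, in line with their place in 1.4.1.

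- Access-site events, from the 72-patient series: "Moderate subcutaneous hemorrhage at the puncture site in 12 patients resolved within 1 week". 12/72 = 16.7%, and 0.167 × 50 = 8.3, about 8 of 50. The exact 95% CI is 8.9% to 27.3%, or about 4 to 14 of 50.
- Skin colour change, same series: "Four of seven patients treated with Embozene showed transient cutaneous color change on the treated knee". 4/7 = 57.1%, with exact 95% CI 18.4% to 90.1%. 0.184 × 50 = 9.2 and 0.901 × 50 = 45.05, so about 9 to 45 of 50.
- The 20-patient series in 1.2.2 reports 65% skin discoloration and 10% plantar paresthesia.

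Let *a* be the access-site proportion and *d* the device proportion. If the two are independent, the share of patients with an event in a pooled category is 1 − (1 − a)(1 − d). Without independence it lies between max(a, d) and a + d.

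- d = 10%: 1 − 0.833 × 0.90 = 25% (bounds 16.7% to 26.7%). The ratio to the device proportion is 25/10 = 2.5.
- d = 65%: 1 − 0.833 × 0.35 = 70.8% (bounds 65% to 81.7%). The ratio is 70.8/65 = 1.09.

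Under independence, the pooled category would show about 1.1 to 2.5 times the device proportion.

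**The case against.** The best defence is that the plan does order a device judgement. Section 7.2.1 says so expressly, the list in 7.3 is introduced as what collection includes and need not be complete, and the AE form is not in the documents. A reader might infer that device attribution is never recorded. The text does not support that: it shows only that no scale is defined and no field is listed.

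A reader might also infer that no device-related AE rate can be derived. That too goes too far. Event descriptions are collected, 9.4.3 and 9.4.4 plan proportions by AE type, and 1.4.1 separates device from catheterization risks. An approximate split by type is possible. What stands is that the split is not prespecified and fails for types on both lists.

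The stated objective is the safety of GAE, and 7.1 describes events secondary to the procedure. Grading on the procedure suits that objective, and a device-related rate is not a planned output. This is fair, and it means that 9.4.4 does not fail on its own terms. It does not answer 7.2.1, 7.6, 7.7 or 7.8, which name the device.

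On 7.6, an event must be both device-associated and unanticipated, and unanticipated device effects have their own form (7.5). Ordinary access-site bleeding and transient skin change are listed risks and would not normally qualify. The illustrative counts therefore say nothing about the volume of FDA reports.

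Finally, the illustration is thin. One input is 4 of 7 patients in native knees. An earlier series in 1.2.2 used 75 µm particles, and this trial uses 100 µm. It supports no forecast.

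**Conclusion.** The point stands as an internal inconsistency with practical consequences. Device relationship is required in 7.2.1, 7.6, 7.7 and 7.8, but it has no defined scale in 7.2.2 and no listed field in 7.3. Section 7.2.2 also gives two standards, and the halting rule uses terms that are not on the scale.

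The limit is that the causality grade as specified cannot isolate device events. It does not follow that no device information will exist.

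The size cannot be fixed from the documents. The factor of 1.1 to 2.5 rests on native-knee rates, on treating skin change and paresthesia as device events, and on independence. It shows direction and rough scale only. The comparison of sections needs none of these assumptions.

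This should be corrected. Attribution by the examining clinician at the time of the event is hard to reconstruct later, and it matters most for the types on both risk lists.

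**What to change.** - **7.2.2, 7.3 and the AE form:** record two separate items, relationship to the study device (microspheres) and relationship to the procedure (access, angiography, sedation). Put both on one defined scale with one standard per category.
- **7.2.2:** remove the sentence that conflicts with Category 3, and the stray reference to study drug administration in Category 1.
- **7.6:** base the device-associated criterion on the device item.
- **9.4.4:** summarise AEs by each relationship item, alongside the planned proportions by type.
- **7.7 and 7.8:** the relatedness terms must be reconciled with the 7.2.2 scale. Which level should count toward a halt is for the sponsor to decide.

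The cost is one extra field per AE and edits to these sections. Some events will be hard to attribute and will be *unknown* on the device item, so the summary should show that count.
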